- 2. Nilson CG Kuuva N, Falconer C, Rezapour M, Ulmsten U, (2001) Long term results of he tension-free vaginal tape (TVT) procedure for the vaginal treatment of female stress incontinence. Int Urogynecol J Pelvic Floor Dysfunct 12(Supple. 2): S5-8.
- 3. Voiding function after Mid-Urethral Slings with and without local anesthetic: Randomized Controlled Trial. UMass IRB H-14197

5) Inclusion and Exclusion Criteria*

Inclusion criteria:

1. Any female subjects scheduled to undergo Mid-Urethral Sling (MUS) through the UMass urogynecology service for incontinence.

Exclusion criteria:

- 1. Planned concurrent prolapse or other procedure besides cystoscopy
- 2. Using intermittent self catheterization preoperatively
- 3. Undergoing spinal anesthesia for the procedure
- 4. Known allergy to phenazopyridine (AKA Pyridium)
- 5. Renal insufficiency
- 6. Any condition or situation that in the attending physician's opinion would contra-indicate the use of phenazopyridine
- 7. Subjects not competent to give consent
- 8. Prisoners
- 9. Non-English or non-Spanish speaking patients
- 10. Age < 18
- 11. Pregnant patients
- 12. Contraindications to the use of IV methylene blue including
 - a) Patients with known hypersensitivity reactions

Page 2 of 10 Revised: 6/30/16 Approved 7/7/16

- b) Severe renal insufficiency
- c) Patients with G6PD deficiency

6) Study-Wide number of Subjects*

N/A not a multicenter study

7) Study-Wide Recruitment Methods*

N/A not a multicenter study

8) Study Timelines*

- Participants will be enrolled in the study for approximately 6 weeks.
- We anticipate 2 years to enroll all the subjects into the study
- Primary analysis will be completed within 6 months after enrollment is completed.

9) Study Endpoints*

- Primary outcome is the rate of voiding dysfunction between the two groups.
- Secondary outcomes include: complications, perioperative pain scores,
- Once 50% of the subjects have completed their procedures, we will perform an interim analysis of the rates of voiding dysfunction. If there is a statistically significant difference (p<0.01) at this interval analysis, we will terminate the study.

10) Procedures Involved*

Study design and randomization

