This study is a randomized controlled trial. Randomization will be performed using software and a block randomization scheme. Study assignment will be completed using sequentially numbered sealed opaque envelopes. All the research procedures described other than the use or not of phenazopyridine will be applicable to both arms of the study. Subjects will have a 50% chances of getting either phenazopyridine or nothing.

Because pyridium turns the urine orange, it is impossible to blind the patients and researchers to the study assignment. Because there is no known placebo that turns the urine orange, there is no value to using an actual placebo tablet. Subjects will be assigned to either receive pyridium or not receive pyridium preoperatively.

Page 3 of 10 Revised: 6/30/16 Approved 7/7/16

Screening potential subjects: Investigators will screen potential subjects for contraindications to methylene blue. Prior obtaining the routine surgical consent for the potential subject's surgical procedure, the patient's medical history in the UMass Electronic Medical Record is routinely reviewed. The medical record will be reviewed for a diagnosis of G6PD and if found, the potential subject will be excluded.

Once written consent has been obtained, subject number will be assigned and the appropriate randomization envelope will be opened. The study assignment will not be formally shared with the subject. Those assigned to the "pyridium" arm will have orders written for the standard 200 mg dose of pyridium to be given on arrival to the Surgical Admissions Care Unit (SACU). Those assigned to the "NO pyridium" arm with have their routine preoperative orders written along with an order for "No preoperative pyridium".

Subjects will then follow the routine perioperative care for their procedures with the only study interventions being the gathering of PHI and performing postoperative pain assessments.

PHI will be obtained at the time of the surgical consent with the purpose to evaluate for possible confounders affecting the postoperative bladder function.

Surgical procedure:

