The Mid Urethral Sling will be performed in standard fashion based on manufacturer's recommendations and instructions to minimize inter-observer variations. We will perform the procedure according to our usual and customary techniques. The subject will receive the same technique and interventions that a routine patient on the Urogyn service would expect to undergo. There will be no changes to the technique for the purpose of the study.

Bladder challenge:

Patient will undergo voiding trial at same day surgery per our usual and customary protocol. This is the same protocol the subject would undergo as a patient on the Urogyn service. The bladder challenge will be interpreted in our usual manner and the subject managed according to our routine clinical protocols.

Postoperative care:

Subjects will undergo routine postoperative care and followup. Subjects failing their bladder challenge will be seen in the Urogyn clinic according to routine clinical protocols and data councerning their void trials collected. Subjects will undergo routine followup evaluation 6 weeks postoperatively in the order to assess any potential long-term voiding dysfunction. Information on any postoperative complications will be collected

Administration of Visual analog scale:

Page 4 of 10 Revised: 6/30/16 Approved 7/7/16

- (1) Visual analog scale for assessment of pain will be administered at two time intervals.
 - (a) VAS #1) Preoperative VAS will be done by the principal investigator or any of the study assistants. The VAS form will be part of subject's packet.
 - (b) **VAS#2)** VAS will be administered by one of the study investigators 2 to 3 hours after the surgical procedure in the SACU.

11) Data and Specimen Banking*

N/A

12) Data Management*

Power Calculation: We used data from the recent "*Urine and Me*" study conducted at UMass. A 20% percent difference in subjects passing the bladder challenge was felt to be clinically significant. In order to capture this difference a power calculation was performed via the Wilcoxon signed-rank test. Based on this, to detect a 20% difference with a α -error = 0.05 and a power (1- β error) = 0.80, a minimum of 41 subjects per group (82 total) will need to be recruited. Assuming ~ 10% dropout rate (8), we will seek to recruit 90 patients.

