Data analysis: Continuous measures will be compared using the unpaired Student's t test. Association between outcome measures and graph assignment will be adjusted according to demographic differences using an analysis of covariance. Standard statistical programs (SAS, SPSS) will be used to determine the mean differences between the voided/catheterize and bladder scanner volumes.

13) Provisions to Monitor the Data to Ensure the Safety of Subjects*

There is minimal risk involved with the denial of pyridium to subjects. Prior to the withdrawal of indigo carmine from the market in 2014, patients did not routinely receive pyridium preoperatively. Currently a minority of surgeons use pyridium in sling procedures with most using nothing. In the event that the ureters need to be assessed for patency, subjects will be given methylene blue to dye the urine. This is the intervention currently used to assess ureters in procedures where ureteral patency is assessed. Thus both groups are receiving care that is considered within the standard of care.

Subjects will be monitored in a similar manner to all of our postoperative patients. There is a chance that pyridium may be beneficial to patients and that denying this medication may result in less desirable outcomes. This study is specifically designed to look at the issue. We plan to perform an interim analysis of the data once 50% of subjects have completed the study and if there is a clear benefit (or harm) from this medication, will terminate the study early and offer the medication to all patients.

Page 5 of 10 Revised: 6/30/16 Approved 7/7/16

14) Withdrawal of Subjects*

Subjects are free with withdraw from the study at any time. If subjects withdraw their participation, any data that has already been collected for research purposes will be destroyed or anonymized so that it can no longer be identified with the subject. There should not be additional data collection of demographic information for research purposes at the time a subject withdraws their consent for the study.

15) Risks to Subjects*

This study poses minimal risk to subjects. Subjects randomized to the pyridium arm will receive pyridium as it is commonly given to patients undergoing reconstructive procedures currently through the Urogyn division at UMass. Subjects denied pyridium will undergo the same procedures and techniques that our patients not in the study will receive.

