One risk from the study is the risk associated with denying subjects preoperative pyridium for their procedure. Because pyridium is used to dye the urine for evaluation of the ureters, in the event there is concern for ureteral injury, patients will be given methylene blue to dye the urine. In addition over the last 5 years and over 300 cases at UMass, there have been no cases where there has been concern for ureteral injury at the time of a midurethral sling placement. In patients undergoing gyn procedures where injury to the ureter is suspected, methylene blue is routinely given to evaluate for ureteral patency. Thus the patients in both arms will be receiving care that is considered standard for these procedures.

Investigators will screen potential subjects for contraindications to methylene blue. Prior obtaining the routine surgical consent for the potential subject's surgical procedure, the patient's medical history in the UMass Electronic Medical Record is routinely reviewed. The medical record will be reviewed for a diagnosis of G6PD and if found, the potential subject will be excluded.

There is a risk of unauthorized disclosure of protected health information. The datasheets will be kept in a locked cabinet in a locked office in the administrative offices of the division on Jaquith 2. The data will be entered into a de-identified, password protected file kept on the departmental computer servers.

16) Potential Benefits to Subjects*

Subjects who receive pyridium may have a lower rate of perioperative voiding dysfunction and a lower rate of perioperative catheterization.

Page 6 of 10 Revised: 6/30/16 Approved 7/7/16

17) Vulnerable populations

N/A

18) Multi-Site Research*

N/A

19) Community-Based Participatory Research*

N/A.

20) Sharing of Results with Subjects*

N/A.

21) Setting

Subjects will be identified and recruited at the urogynecology clinic located at UMass Memorial and the urogynecology clinic at Westborough UMass Memorial Health Care. The urogynecology division has two full time designated surgeons (the PI is one of them) and both will be part of the study. In addition one urogynecology fellow will work as a study assistant. All these three members will participate recruiting subjects and obtaining intraoperative and postoperative data.

There will be no composition or involvement of any community advisory board, and this research will not be conducted outside of UMass or its affiliates.

22) Resources Available

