This research will be conducted through the scheduled urogynecology clinic.

Roles of the members of the study:

- Principal investigator. Identifying potential subjects for the study, consenting of subjects, performing surgical procedures, participating in the data analysis, preparing submissions to the IRB, oversight of the conduct of the study and research personnel.
- Study assistants. Identifying potential subjects for the study, consenting of subjects, assisting in the surgical procedures.
- Biostatistician. The OBGYN Department has a designated biostatistician who will help with the data analysis. The biostatistician will not participate in the recruitment of study subjects.

The PI, co-investigator and all study assistants are CITI-trained. All of them are also clinical members of the urogynecology division at UMass Memorial Medical Center Department of Obstetrics and Gynecology. Before initiation of the research, all study assistants will be instructed on

Page 7 of 10 Revised: 6/30/16 Approved 7/7/16

the protocol and research procedures at the urogynecology department's scheduled bimonthly research meetings.

23) Prior Approvals

N/A

24) Recruitment Methods

Subjects will be recruited through the outpatient Urogynecology clinics of the Urogyn faculty. Patients scheduled to undergo a midurethral slings and meeting criteria will be approached for participation when they present for their preoperative evaluation.

Investigators will screen potential subjects for inclusion and exclusion criteria to the study including contraindications to methylene blue. Prior obtaining the routine surgical consent for the potential subject's surgical procedure, the patient's medical history in the UMass Electronic Medical Record is routinely reviewed. The medical record will be reviewed for a diagnosis of G6PD and if found, the potential subject will be excluded.

Potential subjects will be approached by their surgeon at their preoperative visit. Once eligibility has been confirmed, potential subjects will be offered the opportunity to participate in the study. The study will be reviewed in detail and ample opportunity for questions will be given. The opportunity to decline participation will also be given. For women agreeing to participation, informed written consent will be obtained.

25) Local Number of Subjects

90 subjects will be enrolled in the study.

26) Confidentiality

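### The primary endpoint is an unmasked reading of the bladder challenge with no written pass/fail criterion; classifying recorded volumes without arm codes would remove the classification part of the bias

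*Combined protocol and SAP*

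**What the plan says.** All references are to the combined protocol and SAP.

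- **Endpoint (Section 9).** "Primary outcome is the rate of voiding dysfunction between the two groups". Voiding dysfunction is not defined further. The power paragraph in Section 12 is framed as a difference in subjects passing the bladder challenge, so a failed challenge is the natural reading of the endpoint.
- **Conduct (Section 10, Bladder challenge).** "Patient will undergo voiding trial at same day surgery per our usual and customary protocol". That clinical protocol is not reproduced.
- **Reading (same paragraph).** "The bladder challenge will be interpreted in our usual manner and the subject managed according to our routine clinical protocols". No volume threshold is given and no reader is named.
- **Masking (Section 10, Study design and randomization).** "Because pyridium turns the urine orange, it is impossible to blind the patients and researchers to the study assignment".
- **Personnel (Section 21).** Two surgeons, one of them the principal investigator, and a fellow: "All these three members will participate recruiting subjects and obtaining intraoperative and postoperative data".
- **Volumes (Section 12, Data analysis).** Standard software will be used to "determine the mean differences between the voided/catheterize and bladder scanner volumes". The sentence is not tied to the primary endpoint.
- **Biostatistician (Section 22).** This person helps with the data analysis. "The biostatistician will not participate in the recruitment of study subjects". Masking is not mentioned.
- **Prior result (Section 4).** The investigators report about 28% voiding dysfunction without the drug and 10% with it.

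**The concern.** The plan does specify a method for the endpoint: the clinical service's own reading, made with no masked step. The team has published its expectation of a large benefit in the background section. Where a challenge result is borderline, knowledge of the arm could tip the reading, and the likely direction is toward that expectation.

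The stated reason for not masking is orange urine. That holds for the patient and for anyone at the bedside. It does not hold for a person given a list of volumes by study ID, and Section 27 already stores data under study IDs. The protocol gives no reason against masked classification.

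The stakes are the single primary comparison, and also the interim look at half of subjects, which uses the same readings and can stop the trial.

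**Working it through.** The plan states no figure for this point, so there is none to reproduce. The check has two parts.

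**1. Does the stated reason for not masking cover classification?**
Section 10 rests on urine colour. Section 12 implies that voided, catheterised or scanned volumes are measured. Section 27 keeps data under study ID. A file of study ID and volumes shows neither colour nor arm. Masked classification is therefore feasible if the volumes are captured for every subject and a criterion is written.

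**2. How much could unmasked reading matter?**

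Inputs from the plan: 41 per arm (Section 12), and 28% and 10% (Section 4).
Inputs that are assumptions: no true effect; a true failure rate of 19% in both arms, the midpoint (28 + 10)/2; a borderline share of 10% or 5% of subjects; borderline subjects read as failures 75% of the time in controls and 25% on drug, with 50% as the neutral reading. The plan names no test for this binary comparison, so both uncorrected chi-square and Fisher are shown.

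*Expected events:* 82 × 0.19 = 15.6.

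*Sensitivity to single readings.* With failures a (control) and b (drug), z = ((a − b)/41) / √(p̄(1 − p̄) × 2/41), where p̄ = (a + b)/82. For 15 failures in all, p̄ = 0.183 and the denominator is 0.0854.

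| Failures, control v drug | z | Chi-square p | Fisher p |
|---|---|---|---|
| 10 v 5 | 0.1220/0.0854 = 1.43 | 0.153 | 0.253 |
| 11 v 4 | 0.1707/0.0854 = 2.00 | 0.046 | 0.084 |

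Re-reading one subject in each arm crosses 0.05 by chi-square but not by Fisher.

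*False-positive rate.* Observed rate = clear failures + borderline share × probability of being failed.

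- 10% borderline: clear failures 19% − 10% × 0.5 = 14%. Control 14% + 7.5% = 21.5%; drug 14% + 2.5% = 16.5%.
- 5% borderline: clear failures 19% − 5% × 0.5 = 16.5%. Control 16.5% + 3.75% = 20.25%; drug 16.5% + 1.25% = 17.75%.

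The rejection probability is the sum of Bin(a; 41, p_control) × Bin(b; 41, p_drug) over all pairs (a, b) with two-sided p < 0.05.

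| Scenario | Chi-square, total | Chi-square, favouring drug | Fisher, total | Fisher, favouring drug |
|---|---|---|---|---|
| No reading bias | 5.2% | 2.6% | 2.9% | 1.4% |
| 5% borderline | 6.1% | 4.8% | 3.5% | 2.8% |
| 10% borderline | 9.1% | 8.5% | 5.5% | 5.3% |

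*A second parameterisation* by uncorrected test: if on average one drug-arm failure in 41 is read as a pass, the chance of a false result favouring the drug rises from about 2.5% to 4.4% (true rate 28%) or 4.8% (20%). With two, it is 7.3% or 8.6%.

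**The case against.** Five objections carry weight.

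- **The criterion may exist already.** The routine clinical protocol, which the documents do not show, may hold a strict numeric cut-off. The bedside reading would then be largely mechanical and the assumed 75%/25% split too pessimistic. This stands as a limit on size. It also makes the fix easier, because the rule need only be written down.
- **No reader is named.** A reader might infer that the operating surgeons read the challenge themselves. Section 21 says that they help to obtain postoperative data, which is not the same as interpreting the voiding trial. The point needs only that no masked reader is planned, and that is so.
- **Volume capture is implied, not stated.** The Section 12 sentence could describe a comparison of measurement methods. It does not promise volumes for every subject's first challenge.
- **The resources are not free.** A reader might infer that an uninvolved biostatistician could do this at no cost. Section 22 bars that person from recruitment only and gives them a part in the analysis, so arm codes would have to be withheld during classification. Volume capture and data handling are real, if small, costs.
- **The remedy is partial.** Unmasked patients and staff still generate the volumes through effort, timing, repeat attempts and the decision to catheterise. Masked classification does not touch that.

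None of these supplies a reason to leave the endpoint without a written criterion or a masked step.

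**Conclusion.** The point holds in a limited form. The primary endpoint is an unmasked service reading without a written pass/fail criterion, and a less biased method is available that the masking argument in Section 10 does not exclude. This goes beyond missing detail, because the method that is stated is itself the weaker choice.

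The size is illustrative. With 10% of subjects borderline, the two-sided false-positive rate goes from 5.2% to 9.1% by uncorrected chi-square, or from 2.9% to 5.5% by Fisher. With 5% borderline it is 6.1% or 3.5%. The borderline share and the 75%/25% split have no source in the documents. Under either test the direction is the same, and almost all of the excess favours the drug.

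A reader might go further and infer that bias is certain, or that a few readings will decide the trial. The documents do not support that: they show neither how much discretion the routine reading allows nor which test will be used. The trial can proceed, but its main comparison is exposed to a risk that is cheap to reduce.

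**What to change.** 1. In Section 9, define voiding dysfunction as failure of the first same-day bladder challenge and write in the pass/fail criterion that the service already uses. That such a criterion exists is an assumption. If it is not in a form that can be applied to recorded volumes, the service must put it in that form before any classification. This review proposes no threshold.
2. In Section 10, require the voided and the catheterised or scanned volumes to be recorded for every subject.
3. Have the biostatistician, or another existing team member, apply the criterion to a file of study IDs and volumes without arm codes. Lock the result before unmasking, and do this for the interim look as well as the final analysis.
4. Report the bedside reading as a sensitivity analysis. Patient care continues to follow the bedside reading, unchanged.
5. State in the report that masked classification does not address bias in how the voiding trial was conducted.

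The cost is a short text change in Sections 9 and 10, one derived variable, complete volume capture and some extra data handling. Occasionally a subject's study classification will differ from the bedside decision.

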1) **Title:** The Effect of oral PhenazopyrIdine on Perioperative voiding After mid-urethral sliNg (EPIPhANy study)

2) IRB Review History*

N/A

3) Objectives*

- a) Primary objective: Evaluate the effect of phenazopyridine (brand name Pyridium) on immediate postoperative voiding function in patients undergoing midurethral slings
- b) Secondary objective: Evaluate percent pain reduction with and without use of oral Pyridium at two hours post-procedure.

4) Background*

The midurethral sling (MUS) is a very common, highly successful procedure for the management of stress urinary incontinence due to urethral mobility, with cure rates ranging from 80 to 86%. A common complication of the MUS procedure is short-term postoperative voiding dysfunction. Approximately 20% (7) of patients undergoing MUS are unable to void in the immediate postoperative period and are discharged home with indwelling bladder catheter for 3-5 days. Virtually all patients discharged with a catheter are able to effectively void within 5 days of the procedure and long-term voiding dysfunction is extremely uncommon

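### The postoperative pain score behind the secondary objective is taken by an investigator who is not blinded, and Section 10 does not say who marks the form, whether privately, or whether the baseline precedes randomization

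*Combined protocol and SAP*

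**What the plan says.** Section 3 gives one secondary objective: "Evaluate percent pain reduction with and without use of oral Pyridium at two hours post-procedure". Section 9 also names pain among the outcomes: "Secondary outcomes include: complications, perioperative pain scores".

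Section 10, on study design and randomization, states that because of the orange urine "it is impossible to blind the patients and researchers to the study assignment". On timing it says: "Once written consent has been obtained, subject number will be assigned and the appropriate randomization envelope will be opened". It adds: "The study assignment will not be formally shared with the subject".

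Section 10, on the visual analog scale (VAS), sets two assessments.
- VAS #1: "Preoperative VAS will be done by the principal investigator or any of the study assistants". The form is said to be in the subject's packet.
- VAS #2: "VAS will be administered by one of the study investigators 2 to 3 hours after the surgical procedure in the SACU".

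Section 21 describes the two surgeons and the fellow: "All these three members will participate recruiting subjects and obtaining intraoperative and postoperative data".

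Section 12 plans an unpaired t test for continuous measures.

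**The concern.** A VAS pain score is a subjective self-report, so the way the scale is presented and collected can affect it. The plan gives the collection of VAS #2 to a member of the treating team, in a trial where that team is declared unblinded. The team also has a prior expectation of benefit from the drug: Section 4 reports its own observation of voiding dysfunction falling from about 28% to 10%. That observation concerned voiding, not pain.

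Orange urine explains why there is no placebo. It does not require an investigator at the bedside when the score is given. Section 10 lists the postoperative pain assessments among the few things the study adds to routine care, so how they are done is in the protocol's own hands.

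At stake is whether a difference in pain between arms can be read as an effect of the drug.

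**Working it through.** **Step 1. What the text settles and what it leaves open.**

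| Question | VAS #1 | VAS #2 |
|---|---|---|
| Who gives it? | Principal investigator or a study assistant | A study investigator |
| After the envelope is opened? | Not stated | Yes, since it follows surgery |
| Form stated to be in the packet? | Yes | Not stated |
| Who marks the line? | Not stated | Not stated |
| Marked in private? | Not stated | Not stated |
| Script, independent collector or masked scoring? | None stated | None stated |

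The envelope is opened once consent is obtained at the preoperative stage, and arm-specific orders are then written. By VAS #2 the assignment is known to the team, and nothing provides for an assessor unaware of it. VAS #1 could fall on either side of the opening.

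**Step 2. How this reaches the objective.** Percent reduction for one woman is 100 × (VAS #1 − VAS #2) / VAS #1. VAS #2 enters in every case. If VAS #1 precedes the envelope, knowledge of the arm cannot affect it, and any team influence enters through VAS #2 alone. If it follows, both terms are exposed.

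**Step 3. Sensitivity of the comparison.** The documents give no VAS spread and no size of bias, so there is no plan figure to reproduce. The following is an illustration only.

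Inputs: 41 per arm and α = 0.05 (Section 12, where they were set for the primary outcome); two-sided test; no true drug effect; an assumed shift between arms of b standard deviations caused only by how scores are obtained.

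Standard error in SD units: √(2/41) = 0.221.

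Rejection probability (normal approximation): Φ(b/0.221 − 1.96) + Φ(−b/0.221 − 1.96).

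| Assumed shift b | b/0.221 | False-positive rate |
|---|---|---|
| 0 | 0 | 5% |
| 0.1 SD | 0.45 | 7% |
| 0.2 SD | 0.91 | 15% |
| 0.3 SD | 1.36 | 27% |

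With 45 per arm (all 90 recruits) the last three rates are about 8%, 16% and 30%.

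For scale, if the SD were 2.0 to 2.5 points on a 0–10 line (an assumption), 0.2 SD would be 0.4 to 0.5 points.

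**The case against.** The best reply is that the plan may already do most of what is wanted. A VAS is ordinarily marked by the patient, and giving it may mean no more than handing over and explaining the form. The women may recognise their arm from their urine, so changing who collects the form cannot make the outcome blind. Ward staff carry out the drug orders and may know the arm too. A woman two to three hours after surgery may also need the scale explained.

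Much of this stands, and it rules out several stronger readings that a reader might infer:

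- *Both scores are taken by people who know the arm.* This is shown for VAS #2 only. The text does not date VAS #1 relative to the envelope.
- *The form is already to hand, so no investigator is needed.* The packet is mentioned only under VAS #1. A form in it for VAS #2 is inference.
- *An investigator asks for the score and writes it down.* No section says so. Self-marking is unspecified, not excluded.
- *The false-positive rate is 15% or more.* Any non-zero assumed shift raises it, so the table does not show that bias is likely. It also models a shift in the score in SD units, not percent reduction, whose spread is unknown. If both scores were influenced alike, part of the shift would cancel in a change from baseline.

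The reply does not remove the gap itself. An unblinded investigator is named to give the score that carries the objective, and no safeguard is written down. That the women are not formally told their arm is a further reason to limit contact that could convey it.

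**Conclusion.** The point holds as a cheap improvement to the design. The protocol lets an unblinded member of the study team administer VAS #2 and is silent on who marks it, in what privacy, and on the order of VAS #1 and randomization. Team influence can therefore enter the pain comparison. The documents do not show that it will, or how large it would be; the 7%, 15% and 27% rest wholly on the assumed shifts of 0.1, 0.2 and 0.3 SD.

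The consequence is confined to pain. The primary voiding outcome, the sample size and the interim rule are untouched.

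**What to change.** In Section 10, under the visual analog scale:

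1. State that VAS #1 is completed before the randomization envelope is opened.
2. Put a second form and an envelope in the packet for VAS #2.
3. State that, after a standard neutral explanation, the woman marks the line herself, alone, and seals the form.
4. Have existing ward staff hand over and collect the form. No study investigator prompts, reads or records the score in her presence.
5. Measure the line and enter the value later, from forms identified by subject number only.

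This costs some wording, a second form and an envelope, and needs no added staff. The downside is an occasional form returned unmarked. The change removes only the part of the bias that the team could add. Awareness from orange urine remains, and ward staff may not be masked, so the report should still describe pain as an open-label outcome.
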